Body Imaging	See note		
Only for participants without progression on study therapy. See Section 9.1.1. Imaging assessments will occur every 8 weeks (\pm 7 days) from the date of first dose until disease progression, end of study, or withdrawal of consent, whichever occurs first.
 
For Part 1B and Part 2: Tumor assessment scans should be submitted to the imaging vendor within 14 days of acquisition.

Brain Imaging	See note		
See Section 9.1.1. Participants with a history or clinical symptoms of brain metastasis should have surveillance MRI per local SOC (approximately every 12 weeks) or sooner if clinically indicated.

Other Imaging: Bone Scan	See note		As clinically indicated. See Section 9.1.1.2 .

Table 2-7: Follow-Up Period (All treatment cohorts, CA2099N9)

Procedure ^a	Follow-Up, Visits 1 and 2 ^b	Survival Follow-Up Visits ^c	Notes
Healthcare Resource Use			Per Protocol Amendment 04, the collection of data for Healthcare Resource use must be discontinued.
Participant Status			
Survival Status	X	X	Per Protocol Amendment 04, survival status collection will end at the LPLV date, which is defined in Section 5.1 . Every 6 months after FU 2; may be accomplished by visit, phone contact or email, to assess subsequent anti-cancer therapy.

^a Additional testing or assessments may be performed as clinically necessary or where required by institutional or local regulation.

^b Participants must be followed for at least 100 days after last dose of study treatment. Follow-up visit 1 (FU1) = 30 days from the last dose (\pm 7 days) or coincides with the date of discontinuation (\pm 7 days) if date of discontinuation is greater than 42 days after last dose; Follow-up visit 2 (FU2) = 100 days (\pm 7 days) from last dose. Both Follow Up visits should be conducted in person.

^c Survival Follow Up Visits may be conducted in clinic or via telephone contact: Every 6 Months (\pm 14 days) from FU2. BMS may request that survival data be collected on all treated participants outside of the 6-month specified window. At the time of this request, each participant will be contacted to determine their survival status unless the participant has withdrawn consent for all contact.

^d Urinalysis or urine dipstick. If blood, protein, or leukocytes esterase are positive on the dipstick, microscopic examination of the sediment is required.

Table 2-8:

**On-Treatment REDUCED ASSESSMENTS (Part 2 mCRC 3rd line, TRIPLET, [REDACTED]

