Per Protocol Amendment 04, due to early study closure the last participant last treatment (LPLT) date on CA209-9N9 study will occur approximately 9 months after last participant first treatment (LPFT); and last participant last visit (LPLV) date will occur approximately 12 months after LPFT. When this LPLV date is reached, participants follow-up will be ceased, and all participants will complete the study. Any participant still on treatment after LPLT date who continue to demonstrate clinical benefit will be eligible to receive treatment outside of this study in accordance with Protocol [Section 7.8](#). For Cohort 4 and Cohort 6 participants the total maximum duration of treatment will be 2 years, including the treatment duration on CA209-9N9. For participants in Cohort 5, the treatment will be administered as per the local standard of care. In the event alternative means of supplying study treatment as described in [Section 7.8](#) is not accessible, the study may remain open until such means become available or last participant ends treatment and completes follow-up visits 1 and 2 in accordance with [Table 2-8](#), [Table 2-9](#), [Table 2-10](#), and [Table 2-11](#).

In the **initial dose optimization phase of the study**, which is now completed, both the doublet regimen (Part 1, 3L mCRC) and triplet regimen (Part 1A; 2L mCRC) employed “3+3” design for observation of DLT. The dose-limiting toxicities (DLT) observation period was one cycle for both treatment regimens, ie, 4 weeks for the doublet regimen; 8 weeks for the triplet regimen. DLT observations are described in [Section 5.1.1.1](#). Dose optimization phase of the study (Part 1 and Part 1A) has been completed. Enrollment is closed in Part 1 and Part 1A cohorts. No further evaluations of DLT will be conducted.

Participants were allocated to treatment as follows:

- Part 1: Participants with 3L mCRC were assigned to receive doublet therapy as nivolumab 480 mg Q4 week plus trametinib 1.5 mg QD (continuous dosing, Cohort 1 Group)
- Part 1A: Participants with 2L mCRC were assigned to receive the triplet therapy of either:
 - 6 mg/kg nivolumab (Q4W) plus ipilimumab 1 mg/kg (Q8W) plus trametinib 1.5 mg QD (continuous dosing, Cohort 2 Group), OR
 - 6 mg/kg nivolumab (Q4W) plus ipilimumab 1 mg/kg (Q8W) plus trametinib 1.5 mg QD (2 week ON/2 week OFF, Cohort 3 Group)

Only pMMR/MSS participants were enrolled in Part 1 and Part 1A.

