5.3 End of Study Definition

The start of the trial is defined as the first visit for first participant screened. End of trial is defined as the last visit or scheduled procedure shown in the schedule of activities (see [Section 2](#)) for the last participant. Study completion is defined as the final date on which data for the primary endpoint is expected to be collected.

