6 STUDY POPULATION

For entry into the study, the following criteria MUST be met. As of 30-Nov-2022, enrollment into this study was closed.

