8.1.6 Post Study Treatment Study Follow-up

Post study treatment follow-up is of critical importance and is essential to preserving participant safety and the integrity of the study. Participants who discontinue study treatment must continue to be followed until the LPLV on the study.

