9.2.1 Time Period and Frequency for Collecting AE and SAE Information

The collection of nonserious AE information should begin at initiation of study treatment until the time points specified in the Schedule of Activities ([Section 2](#)).

Sections 5.6.1 and 5.6.2, in the IB represent the Reference Safety Information to determine expectedness of serious adverse events for expedited reporting. Following the participant's written consent to participate in the study, all SAEs, whether related or not related to study drug, must be collected, including those thought to be associated with protocol-specified procedures.

All SAEs must be collected that occur during the screening period and within 100 days of discontinuation of dosing. If applicable, SAEs must be collected that relate to any later protocol-specified procedure (eg, a follow-up skin biopsy).

For participants assigned to treatment and never treated with study drug, SAEs should be collected for 30 days from the date of treatment assignment.

The investigator must report any SAE that occurs after these time periods and that is believed to be related to study drug or protocol-specified procedure.

- Medical occurrences that begin before the start of study treatment but after obtaining informed consent will be recorded on the appropriate section of the eCRF section.
- All SAEs will be recorded and reported to Sponsor or designee within 24 hours, as indicated in [Appendix 3](#).
- The investigator will submit any updated SAE data to the sponsor within 24 hours of this being available.

Investigators are not obligated to actively seek AEs or SAEs in former study participants. However, if the investigator learns of any SAE, including a death, at any time after a participant has been discharged from the study, and he/she considers the event reasonably related to the study treatment or study participation, the investigator must promptly notify the sponsor.

The method of evaluating, and assessing causality of AEs and SAEs and the procedures for completing and reporting/transmitting SAE reports are provided in [Appendix 3](#).

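### Does the planned closing timetable cut off the 100-day safety follow-up?

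*Combined protocol and SAP*

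**What the plan says.** The closing timetable is in Section 5.1 and, in the same terms, in the Synopsis. It says that "the last participant last treatment (LPLT) date on CA209-9N9 study will occur approximately 9 months after last participant first treatment (LPFT"), and that the "last participant last visit (LPLV) date will occur approximately 12 months after LPFT. When this LPLV date is reached, participants follow-up will be ceased". The same paragraph has a contingency for the case where no other drug supply is accessible: "the study may remain open until such means become available or last participant ends treatment and completes follow-up visits 1 and 2". Section 8.1.6 adds: "Participants who discontinue study treatment must continue to be followed until the LPLV on the study".

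The follow-up requirements are elsewhere:

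- **Table 2-7, footnote b** (repeated under Table 2-11): "Participants must be followed for at least 100 days after last dose of study treatment". FU1 is at day 30 and FU2 at day 100, each ± 7 days and in person.
- **Section 8.1**: all participants who discontinue treatment are to comply with the follow-up in Section 2. The sole exceptions are withdrawal of consent for study procedures and loss of the ability to consent freely.
- **Section 9.2.1 and Appendix 3**: serious events are collected for 100 days, and non-serious events for at least 100 days. After that, "The investigator must report any SAE that occurs after these time periods and that is believed to be related to study drug".
- **Section 5.3**: "End of trial is defined as the last visit or scheduled procedure shown in the schedule of activities", for the last participant.

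Section 6 states: "As of 30-Nov-2022, enrollment into this study was closed". The LPFT date itself is not given.

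**The concern.** Twelve months minus nine months is three months, and three months is less than 100 days. Someone who took a last dose on the LPLT date would not reach day 100, or even the earliest permitted FU2 day, before the nominal LPLV date. Section 5.1 says follow-up stops when that date arrives. Completion of FU1 and FU2 is named as a closing condition only in the supply contingency, so a reader could infer that the ordinary closure has no such condition.

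If sites took different readings, some participants would leave before FU2 and others after it, and the adverse event collection period would not be uniform. Safety is a secondary objective of Parts 1B and 2, so the question is a fair one to ask.

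**Working it through.** **Inputs.** LPLT is about month 9 and LPLV about month 12 after LPFT (Section 5.1). Minimum follow-up is 100 days, with FU2 on days 93 to 107 (Table 2-7). The plan gives no LPLT-to-LPLV interval in days to reproduce; the implied figure is about 3 months.

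**Nominal interval.** With average months, 3 × 365.25/12 = 91.3 days. With calendar months, it is 89 to 92 days depending on the LPFT date.

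| Target | Shortfall, average months | Shortfall, calendar range |
|---|---|---|
| Day 93 (earliest FU2) | 93 − 91.3 = 1.7 days | 1 to 4 days |
| Day 100 | 100 − 91.3 = 8.7 days | 8 to 11 days |
| Day 107 (latest FU2) | 107 − 91.3 = 15.7 days | 15 to 18 days |

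**Likely dates (assumption).** Enrollment closed on 30-Nov-2022. Suppose LPFT fell 0 to 31 days later (28 days of screening plus 3 days to first dose).

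- LPFT 30-Nov-2022: LPLT 30-Aug-2023, LPLV 30-Nov-2023. The gap is 92 days, 8 short of day 100.
- LPFT 03-Dec-2022: LPLT 03-Sep-2023, LPLV 03-Dec-2023. The gap is 91 days, 9 short.
- LPFT 31-Dec-2022: LPLT 30-Sep-2023, LPLV 31-Dec-2023. The gap is 92 days, 8 short.

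**If LPLV waits for FU2.** With 30.44 days per month:

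- Day 93: 9 + 93/30.44 = month 12.06
- Day 100: 9 + 100/30.44 = month 12.29
- Day 107: 9 + 107/30.44 = month 12.52

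A target of about 12 months can accommodate all three.

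**Who could be affected.** A participant last dosed k days before LPLT reaches day 100 by the nominal LPLV if k is at least 100 − 91.3 = 8.7. Only those whose last on-study dose falls within about 9 days before LPLT (about 16 days if FU2 is done on day 107), and who do not continue treatment outside the study, could fall short. The documents do not give their number.

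**Effect on response.** Scans are every 8 weeks from first dose. By month 12 (about 52 weeks) the last participant to start is scheduled for six, at weeks 8 to 48. Waiting for FU2 moves LPLV to (9 × 30.44 + 100)/7 = 53.4 weeks, or 54.4 weeks at day 107. The week-56 scan opens at week 55, so neither date adds a scheduled scan for that participant.

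**The text read together.** Section 8.1 lists its exceptions to scheduled follow-up, and reaching LPLV is not one of them. Footnote b is a minimum, and the 100-day collection periods in Section 9.2.1 and Appendix 3 are not shortened at LPLV. Section 5.3 ends the trial at the last scheduled visit or procedure, and FU2 is such a visit. LPLV is by name the last participant's last visit, so an outstanding required visit belongs to it. Section 8.1.6 is a duty to keep following people who stopped earlier; it does not waive FU2.

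**The case for a change.** The best case for a change is that none of this appears in one sentence. The word approximately does not tell a site whether the LPLV date or FU2 governs, and Section 5.1 does say that follow-up stops on that date. The ± 7 days applies to the FU2 visit, not to the 100-day minimum or to the event collection periods. The affected group is not fanciful: trametinib is taken daily, so a triplet participant on uninterrupted treatment at LPLT has a last on-study dose at or just before it. For those who continue treatment outside the study, nothing says when the 100 days begin. One sentence would cost almost nothing.

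What stands is that the sentence is missing and would be tidy. The rest is weaker. Naming FU1 and FU2 in the contingency does not remove them from the ordinary closure: Table 2-11, which serves the contingency, has no survival follow-up column, so FU2 is the last visit there and the natural closing point. Table 2-7 goes on to survival follow-up and uses LPLV to end it. For participants treated afterwards, Table 2-7 counts from the last dose of study treatment, and Section 7.8 describes the later supply as study treatment given through an extension, a rollover study or another mechanism. Follow-up of those later doses would largely belong to that mechanism. The exact start of the clock remains unstated, and no consequence for this study's results has been shown.

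**Conclusion.** No change is needed. The subtraction is right, but it sets two rounded month figures against an exact day count, so it shows loose wording and not an arithmetic error. A team following the plan's own 100-day requirements would complete FU2 and let LPLV fall at about month 12.3.

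On a literal reading, the most that could be lost is 8 to 11 days of event collection (8 or 9 on the assumed LPFT dates) in participants last dosed within that many days before LPLT whose treatment ends on the study. Related serious events remain reportable after the collection period, and treatment-related toxicities are followed until they resolve, return to baseline or are deemed irreversible. That leaves mainly non-serious or unrelated events at risk. The size of the group is unknown and could be zero. The primary endpoint of Parts 1B and 2 is unaffected, and no change in any reported result has been shown.

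This rests on reading Sections 5.1 and 8.1.6 together with Table 2-7 and Sections 5.3, 8.1 and 9.2.1, and on the assumed LPFT range where specific dates are given.

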5.1.4 Data Monitoring Committee and Other External Committees

A data monitoring committee (DMC) will not be utilized for this Phase 1/2 study.

5.1.4.1 Blinded Independent Central Review

A blinded independent central review (BICR) may be utilized in Part 2 and Part 1B of this study [REDACTED]. Details of BICR procedures will be specified in a BICR Charter. Refer to [Section 9.1.1 Imaging Assessment for the Study](#) for further details.

5.2 Number of Participants

Part 1 and Part 1A followed a 3+3 design, with potential dose escalation and de-escalation based on DLT observations, with intention to treat up to approximately 18 and 24 participants, respectively. Part 1 and Part 1A (dose optimization phase) have completed. Part 1B, will treat approximately 80 participants. Part 2 will randomize approximately 120 participants into 2 arms (nivolumab + ipilimumab + trametinib and regorafenib) in a 2:1 ratio. See [Section 10.1](#) for sample size determination.

5.3 End of Study Definition

The start of the trial is defined as the first visit for first participant screened. End of trial is defined as the last visit or scheduled procedure shown in the schedule of activities (see [Section 2](#)) for the last participant. Study completion is defined as the final date on which data for the primary endpoint is expected to be collected.

5.4 Scientific Rationale for Study Design

5.4.1 Rationale for 2 year treatment duration for Immunotherapy (Nivolumab + Ipilimumab)

The optimal duration of immunotherapy is an important question and continues to be investigated. Clinical trials across different tumor types in the nivolumab and ipilimumab development program indicate that most of the responses occur early, with a median time to response of 2 to 4 months, and emerging data suggests that benefit can be maintained in the absence of continued treatment. A recent analysis in a melanoma study suggests the majority of patients who discontinue nivolumab and/or ipilimumab for toxicity maintain disease control in the absence of further treatment.⁹² Furthermore, a limited duration of ipilimumab (at doses up to 10 mg/kg), including

only 4 induction doses, resulted in long term survival in patients with metastatic melanoma, with a sustained plateau in survival starting around 2 years after the start of treatment.⁹³

Accumulating data suggest that 2 years of PD-1 checkpoint inhibitor treatment may be sufficient for long term benefit. CA209-003, a dose-escalation cohort expansion trial evaluating the safety and clinical activity of nivolumab in patients with previously treated advanced solid tumors (including 129 subjects with NSCLC), specified a maximum treatment duration of 2 years. Among 16 subjects with NSCLC who discontinued nivolumab after completing 2 years of treatment, 12 subjects were alive > 5 years and remained progression-free without any subsequent therapy. In the CA209-003 NSCLC cohort, the OS curve begins to plateau after 2 years, with an OS rate of 25% at 2 years and 18% at 3 years.⁹⁴ These survival outcomes are similar to Phase 3 studies in previously treated NSCLC, in which nivolumab treatment was continued until progression or unacceptable toxicity (2 year OS rates of 23% and 29%, and 3 year OS rates of 16% to 18% for squamous and non-squamous NSCLC, respectively).⁹⁵

Taken together, these data suggest that treatment beyond 2 years is unlikely to confer additional clinically meaningful benefit and that the risk of progression after discontinuing treatment at 2 years is low.

In contrast, a shorter duration of nivolumab of only 1 year was associated with increased risk of progression in previously treated patients with NSCLC, suggesting that treatment beyond 1 year is likely needed. In CA209153, patients with previously treated advanced NSCLC who completed 1 year of nivolumab therapy were randomized to either continue or stop treatment, with the option of retreatment upon progression. Among 163 patients still on treatment at 1 year and without progression, those who were randomized to continue nivolumab had significant improvement in progression-free survival (PFS) compared to those who were randomized to stop treatment, with median PFS (post-randomization) not reached vs 10.3 months, respectively; HR = 0.42 (95% CI, 0.25 to 0.71). With a median follow-up of 14.9 months post-randomization, there also was a trend for patients on continued treatment to live longer (OS HR = 0.63 [95% CI: 0.33, 1.20]). Of note, the PFS curves in both groups plateau approximately 1 year after randomization (ie, 2 years after treatment initiation), suggesting that there may be minimal benefit in extending treatment beyond a total of 2 years.⁹⁶

Collectively, these data suggest that there is minimal if any benefit derived from continuing I-O treatment beyond two years in advanced tumors. However, even though immunotherapy is well tolerated, patients will be at risk for additional toxicity with longer term treatment. Therefore, in this study, nivolumab treatment will be given for a maximum of 2 years from the start of study treatment.

For these reasons, in study CA2099N9, nivolumab and ipilimumab treatment will be given for up to 2 years in the absence of disease progression or unacceptable toxicity for the doublet and triplet regimens. There is no maximum treatment duration for the SOC arm (regorafenib) in Part 2, Cohort 5, which may be continued until progression of disease or unacceptable toxicity. Please refer to [Section 7.8](#).

5.4.2 Rationale for Choice of Standard of Care Treatment in Part 2

Regorafenib is a standard late line therapy for mCRC patients who have been previously treated with fluoropyrimidine-, oxaliplatin-, and irinotecan-based chemotherapy, an anti-VEGF therapy, and anti-EGFR therapy (if KRAS wild type). Regorafenib is approved by regulatory authorities in many regions of the world for patients with mCRC who have failed at least 2 prior lines of therapy (no more than 4 prior lines).

Regorafenib was chosen to be the SOC treatment in Part 2, in accordance with current clinical expert guidance that advises that regorafenib may provide benefit when used in the 3L+ setting. Prior TAS-102 is allowed as it is often well-tolerated and equally effective whether or not patients have received regorafenib.^{97,98,99,100}

5.4.3 Rationale for Stratification in Part 2

Two stratification factors, primary tumor location (right vs left sided tumor) and extended RAS mutation status (wild-type vs mutant) were chosen for the evaluation of the triplet regimen (nivolumab plus ipilimumab plus trametinib) with SOC therapy (regorafenib) in 3L+ (no more than 4 prior lines of therapy) mCRC.

Right vs Left Sided Tumor:

In a systemic review and meta-analysis with more than 1.4 million colon cancer participants, a significant prognostic impact of primary tumor location on overall survival (OS) was observed with a 20% reduced risk of death for cancers arising on the left side.¹⁰¹ Such a survival benefit seen in the left side primary tumor was independent of disease stage (II, III, and IV), and Stage IV disease showed a significantly greater survival benefit compared with Stage II and III disease. Recent meta-analysis based on data from 6 randomized clinical trials in mCRC (Stage IV), CRYSTAL, PRIME, PEAK, FIRE-3, CALGB 80405 and 20050181, also demonstrated predictive favorable effect on OS and PFS in patients with left-sided tumors.¹⁰² Five of the aforementioned studies were in 1L mCRC patient population, and Study 20050181 was in the 2L mCRC patient population.

Thus, the right versus left sided tumor is chosen as one of the 2 stratification factors. Specifically, primary tumors originating in the appendix, cecum, ascending colon, hepatic flexure, and transverse colon will be classified as right-sided. Primary tumors originating in the splenic flexure, descending colon, sigmoid colon, rectosigmoid junction, and rectum will be classified as left-sided. If tumors were located in both left-sided and right-sided locations and the origin could not be ascribed to either side, these tumors will be stratified as right-sided (Appendix 13).

Participants with unknown primary tumor location or primary tumor located in both sides will be stratified to the right-sided stratum. Such participants are not expected to exceed 2% to 5%.

Extended RAS/BRAF Wild-type vs Mutant:

Extended RAS (KRAS and NRAS) and BRAF mutation status testing is standard practice in guiding treatment decisions in mCRC. As discussed in [Section 3.2.2](#), the prognostic value of KRAS mutations in mCRC (independent of anti-EGFR therapy) is unclear due to conflicting data from various meta-analyses across all disease stages. It is also uncertain which mutation status will benefit more from the triplet (nivolumab + ipilimumab + trametinib). Based on current available data, preliminary anti-cancer efficacy using PD-L1 antibody in combination with MEKi was observed only in KRAS mutant participants, recognizing 20 out of 23 participants treated were KRAS mutant (refer to [Section 3.1.2](#) for updated results).¹⁰³ In addition, the CORRECT⁴⁵ and RE COURSE trial results also indicated that both regorafenib and TAS-102 improved OS over best supportive care numerically higher in the KRAS wild-type population than in the KRAS mutant population, although not statistically significant. In order to keep balanced distribution of each treatment stratum for both cohorts (Cohort 4 and Cohort 5), extended RAS mutation status will also be utilized as a stratification factor in Part 2. Coexistence of both RAS and BRAF mutation is very rare. Thus participants whose tumors are wild-type for extended RAS vs. participants whose tumors are extended RAS mutant will be stratified into 2 groups, RAS wild-type vs mutant. Capping for wild-type (extended RAS) status will be implemented per study design ([Section 5.1](#)). BRAF mutations are observed in 5% to 10% of CRC, with 80% to 90% of BRAF mutations being V600E.^{40,104} Given the poor prognosis associated with BRAF V600 mutations, these patients will be excluded.⁴⁰

